## **1. Background**

Primary sclerosing cholangitis (PSC) is a rare cholestatic disorder with a prevalence of 16.2 per 100,000 population; it is characterised by progressive inflammation and destruction of the intra and/or extrahepatic bile ducts culminating in progressive fibrosis and cirrhosis(1-3). It most commonly affects men between the ages of 30- 40 and occurs in the presence of inflammatory bowel disease. It can be detected as part of patient evaluation in IBD or can present with fatigue, abdominal pain, pruritus or jaundice (4). The aetiology of PSC is unclear but may involve cholangiocyte injury resulting from an abnormal immune response to environmental exposure in genetically susceptible individuals (3, 4). Patients with PSC are at risk of both benign and malignant biliary obstruction. Worsening cholangitis with fever, pain and jaundice should prompt further investigation. Poor prognostic factors in PSC include extensive biliary strictures, recurrent cholangitis, evidence of liver synthetic dysfunction and dominant strictures (4). There is no effective medical therapy that has been shown to alter the natural history of the disease. Treatment revolves around managing symptoms and complications as they arise. Trials into medical therapy are currently focused on cholestatic and fibrotic targets (4). Liver transplantation is currently the only therapeutic approach for eligible patients with end-stage disease, but disease recurrence in the graft can be as high as 25% (3).

Clinically significant biliary strictures occur in 45- 65% of patients with PSC (5, 6). Strictures are classified as high grade on MRCP with 75% reduction of duct diameter in the common bile duct or hepatic ducts(6). Patients with new or worsening bile duct stricture with or without signs/symptoms suspicious of malignancy should undergo ERC (4, 5). Symptoms include cholangitis, progressive jaundice and pruritus with evidence of progressive bile

duct dilatation on imaging. Patients who develop high grade, clinically relevant strictures have an increased risk of cholangiocarcinoma, which can occur in up to 26% of patients with significantly reduced overall survival compared to those without high grade strictures (7). High grade strictures should be interrogated via ERC to investigate for the presence of a malignant stricture with tissue obtained via brushings for cytology and consideration of cholangioscopy and biopsy, which has higher sensitivity with comparable specificity (6, 8, 9).

In patients undergoing stenting in PSC, plastic stents are the primary intervention. These small-diameter stents can develop biofilms and occlude over time, possibly leading to cholangitis (10). Biodegradable stents are increasingly being used in a variety of indications (11, 12). They are a novel alternative that may confer benefit in the reduction of treatment-related adverse events by removing the necessity of repeat procedures for stent removal. They are made of polydioxanone (a synthetic biodegradable polymer). These stents have been clinically effective and safe in patients with symptomatic biliary obstruction (12, 13). They hydrolyse with variable degradation times. Similar to plastic stents, they have an introducer that allows placement over the target area, and positioning can be visualised fluoroscopically. The Archimedes stent is a commercially available biodegradable stent produced by AMG International (14). Clinical utilisation of these stents demonstrating excellent safety and efficacy are now emerging (12, 13).

In patients with PSC, endoscopic therapy of strictures aims to improve cholestasis by relieving the biliary obstruction via endoscopic biliary dilatation with consideration of plastic stents in strictures refractory to dilatation due to the risk of pancreatitis and cholangitis (15-17). Short term stents have been shown to have similar recurrence-free

rates compared to dilatation in a randomised control trial; however, this was terminated after interim analysis due to higher rates of serious adverse events in the stent group (15). The long term benefits are unclear; however, it may lead to improved survival compared to predicted survival (18). In this group of patients with limited treatment options, biodegradable stents may provide an attractive additional treatment modality in the management of high grade strictures.

## **2. AIMS**

### **Research hypothesis**

The use of biodegradable stents leads to remodelling of high grade strictures in patients with PSC with fewer interventions in comparison to balloon dilation alone with a comparable risk profile to current therapy.

### **Primary endpoint**

Technical success and safety of biodegradable stent placement at ERC

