### **Secondary endpoints**

- Cumulative recurrence -free rate of primary high grade strictures within 12 months
- Change in symptoms as assessed by the Amsterdam cholestatic complaints score (ACCS)(19)
- Clinical success is defined by improvement in liver function tests (LFT) by 20% at week 2 and week 12.
- Improvement in quality of life as assessed by the Short form-36 (SF-36).
- Mortality, morbidity, local complications, stricture recurrence, decompensation of liver disease, liver transplantation over 12 months.

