### **3. Methods**

#### **Study design**

Single centre, open-label, single group pilot study with a follow up of 12 months.

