#### **Sample size**

A prospective study (15) demonstrated a re-intervention free rate of 55% at 12 months for balloon dilatation. Assuming the re-intervention free survival rate at 12 months would be 55% for balloon dilatation (Group B) vs 15% for short term stenting with a biodegradable stent (Group A) yielded a sample size of  $n = 21$  per group. Allowing for a drop out rate of 15%, rendered a total sample size of 50 to attain a power of 80% and a 2-sided alpha level of 0.05. An interim analysis is planned when 50% of the intended total number of study subjects had passed their 3-month visit. We aim to enroll 21 prospective patients into Group A and use a historical cohort for Group B (undergone balloon dilatation in the last 5 years at King's College Hospital). A sample size of 21 was calculated (confidence 0.90, probability 0.1).

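### The stated 80% power is for 12-month re-intervention-free survival against a historical group, an outcome that is neither the primary endpoint nor named among the secondary endpoints

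*Protocol*

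**What the plan says.** - **Protocol, Primary endpoint:** "Technical success and safety of biodegradable stent placement at ERC". No expected rate, threshold or precision is attached.
- **Protocol, Secondary endpoints:** the nearest items to the powered outcome are "Cumulative recurrence -free rate of primary high grade strictures within 12 months" and a composite list, "Mortality, morbidity, local complications, stricture recurrence, decompensation of liver disease, liver transplantation over 12 months". Neither names re-intervention, and recurrence is not defined.
- **Protocol, Study design:** "Single centre, open-label, single group pilot study with a follow up of 12 months".
- **Protocol, Sample size:** "Assuming the re-intervention free survival rate at 12 months would be 55% for balloon dilatation (Group B) vs 15% for short term stenting". Patients given the biodegradable stent form Group A, and the result is 21 per group. Then: "Allowing for a drop out rate of 15%, rendered a total sample size of 50 to attain a power of 80" per cent, at two-sided alpha 0.05. The section goes on to plan 21 prospective patients in Group A, with past balloon-dilatation patients from the same hospital as Group B. It closes with a second justification of 21, a confidence of 0.90 and a probability of 0.1, without saying what these refer to.
- **Protocol, Research hypothesis:** fewer interventions than balloon dilatation alone, "with a comparable risk profile to current therapy". No adverse-event rate and no margin is given.

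**The concern.** Four parts of the protocol should describe one study and do not. The hypothesis is comparative, the design is labelled as one group, the primary endpoint is descriptive, and the sample size is for a two-group test of an outcome that no endpoint names.

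Two things are at stake. First, a reader who sees 80% power will attach it to the primary endpoint, where it does not apply. The comparison it does apply to has no place in the endpoint list, so nothing fixes what is to be compared with Group B. Second, the hypothesis invites a statement about comparable risk with no yardstick for it. The Background section says that a randomised trial of short-term stents against dilatation was stopped after an interim analysis because of more serious adverse events with stents, so safety is the result that readers will look at most closely.

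**Working it through.** **1. Reproduce the plan's figure.** Inputs from Sample size: 55% and 15%, two-sided alpha 0.05, power 80%, 15% dropout.

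- Arcsine method: n = 2(1.960 + 0.842)² / h², with h = 2·asin√0.55 − 2·asin√0.15 = 0.876. This gives 20.5, so 21 per group.
- Pooled normal formula: 22 per group; power with 21 per group is 79.8%.
- Dropout: 42 / (1 − 0.15) = 49.4, so 50 in total.

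The stated 21 and 50 therefore come from the re-intervention-free comparison, and the 80% belongs to it alone.

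**2. Look for that outcome among the endpoints.** The primary endpoint is technical success and safety. The secondary endpoints are a recurrence-free rate, a symptom score, liver tests, quality of life, and a list of clinical events that includes stricture recurrence. Re-intervention is not named.

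**3. The second basis for 21.** The protocol does not explain it. Read as event detection (an assumption), the chance of seeing at least one event of 10% frequency is 1 − 0.9²¹ = 89.1%. Reaching 90% needs ln 0.1 / ln 0.9 = 21.9, so 22. On this reading the figure is about right, but it concerns seeing one event and does not support a comparison of risk.

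**4. What 21 patients give on the primary endpoint** (exact Clopper-Pearson, two-sided 95%):

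- Technical success 20/21: 76.2% to 99.9%; 19/21: 69.6% to 98.8%.
- Safety events 0/21: upper limit 1 − 0.025^(1/21) = 16.1%; 2/21: 1.2% to 30.4%.

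**5. Comparable risk.** The protocol gives no rate or margin, so both are assumed here. The true rate p is taken as equal in the two groups, with margin m, one-sided alpha 0.025 and 21 per group:

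- n per group for 80% power = (1.960 + 0.842)² · 2p(1 − p) / m²
- power = Φ( m / √(2p(1 − p)/21) − 1.960 )

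| Assumed rate | Margin (points) | n per group for 80% | Power at 21 per group |
|---|---|---|---|
| 5% | 10 | 75 | 32% |
| 10% | 10 | 142 | 19% |
| 20% | 10 | 252 | 13% |
| 5% | 15 | 34 | 61% |
| 10% | 15 | 63 | 37% |
| 20% | 15 | 112 | 23% |
| 5% | 20 | 19 | 84% |
| 10% | 20 | 36 | 58% |
| 20% | 20 | 63 | 37% |

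Only the 5% rate with a 20-point margin reaches 80%, and that margin would tolerate a rise from 5% to 25%. These are normal approximations and are rough at such small counts.

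**6. Two inconsistencies within Sample size.** As written, 15% re-intervention-free on the stent against 55% on balloon dilatation predicts a worse result for the stent, against the hypothesis. And a total of 50 implies 25 per group, whereas 21 are to be enrolled in Group A. After 15% dropout, 21 × 0.85 = 17.9, about 18, remain; with 18 in each group the power is about 73%.

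**The case against.** The strongest reply is that this is a pilot. A pilot may report feasibility and safety descriptively and needs no power for them, and the analysis of the primary endpoint may sit in an SAP that is not at hand. That stands as far as it goes: leaving the choice of confidence interval to the SAP would be no fault. But the protocol itself claims 80% power and states a comparative hypothesis, and the mismatch lies between its own sections.

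It can also be said that the powered outcome is not foreign to the study. The hypothesis speaks of fewer interventions. The protocol also cites the same trial for recurrence-free rates in Background and for a re-intervention-free rate in Sample size, so it may be using two terms for one concept. This is fair. A reader might infer that recurrence is an imaging finding and so a different event from re-intervention, but no section defines recurrence that way. The week 52 MRCP is scheduled to assess remodelling. What stands is that the terms differ and neither is defined as an endpoint matching the power calculation.

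The closing sentence of Sample size may be meant as the basis for the safety endpoint, so it would be wrong to say that 21 has no other justification. It names no endpoint, however, and the reader cannot tell.

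**Conclusion.** The point holds in a limited form and should be fixed. The 80% power applies to a two-group comparison of 12-month re-intervention-free survival. It does not apply to the primary endpoint, or to any secondary endpoint as named. That much rests on the protocol's text and on the reproduction of 21 and 50.

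Two stronger conclusions are tempting, and the protocol does not support them:

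- A reader might infer that the primary result will be reported as proof of comparable risk. The primary endpoint has no margin, test or decision rule, and no section says this.
- A reader might infer that 21 patients can never show comparability. That depends on a margin the protocol does not state; the one very wide case in the table would be met.

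What can be said is that zero events in 21 leaves a true rate of up to 16.1%. Under the assumed rates of 5% to 20% with a 10-point margin, or 10% with a 15-point margin, power for comparability is 13% to 37%. The data can describe the risk; without a stated rate and margin they give no basis for calling it comparable.

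**What to change.** 1. In Secondary endpoints, add re-intervention-free survival at 12 months, defined and compared with Group B. Alternatively, state that it is the same as the recurrence-free rate and define that. In Sample size, say that the 80% power refers to this comparison only.
2. Reconcile the 55% and 15% assumptions with the direction of the hypothesis, and reconcile the 21 to be enrolled with the dropout-inflated total of 50.
3. State that the primary endpoint is estimated, not powered. Give the precision at 21 (for example 19/21 successes, 70% to 99%; 0/21 events, upper limit 16%). Say what the confidence of 0.90 and probability of 0.1 refer to, or delete that sentence.
4. In Study design, describe the study as single-arm with a historical control. In Research hypothesis, limit the safety aim to describing the risk profile.

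**Cost:** protocol wording, and a more modest safety claim. Enrolment changes only if the sponsor settles item 2 by keeping the dropout allowance, which would mean 25 rather than 21 in Group A.

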### **Secondary endpoints**

- Cumulative recurrence -free rate of primary high grade strictures within 12 months
- Change in symptoms as assessed by the Amsterdam cholestatic complaints score (ACCS)(19)
- Clinical success is defined by improvement in liver function tests (LFT) by 20% at week 2 and week 12.
- Improvement in quality of life as assessed by the Short form-36 (SF-36).
- Mortality, morbidity, local complications, stricture recurrence, decompensation of liver disease, liver transplantation over 12 months.

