A high grade stricture is defined as a biliary stricture on MRCP with > 75% reduction of the duct diameter in the common bile duct or hepatic ducts. A relevant stricture is a high-grade biliary stricture on imaging in the common bile duct or hepatic ducts with signs or symptoms of obstructive cholestasis (rise in liver bloods tests, itch) and/or bacterial cholangitis.

All ERC and stent insertion attempts are to be carried out by an experienced operator. All procedures are to be carried out under general anaesthetic as per unit protocol. Medium degradation stents only to be used. All patients will receive intravenous Tazocin 4.5g pre/peri-procedure followed by 2 doses after. In the event of a penicillin allergy, intravenous Ciprofloxacin 500mg will be given with 2 further doses post procedure. All patients will be considered for pre/peri-procedural NSAID.

Patient information and informed consent will be obtained at ERC preassessment alongside physical examination and liver biochemistry. Insertion of the stent via ERC with endoscopist questionnaire on ease of placement, visibility on fluoroscopy, the maximum diameter of the stricture, whether dilatation was used and any procedure-related complications. Patient follow up on day one post insertion with questionnaires with a structured interview to assess for procedure-related symptoms and post-insertion AE. Liver function tests and telephone consultation on week 2 (up to 14 days post procedure) to assess for stent degradation, clinical response to therapy, complications and morbidity. MRCP at week 52 to assess for stricture remodelling with improvement in liver biochemistry. Patients will be closely monitored with access to the clinical team involved in the study. The pilot study will be carried out over 24 months.

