### **Stenting**

A 6Fr Archimedes (medium degradation) stent will be used for for strictures at the biliary hilum with consideration of bilateral stents if possible. 8Fr or 10Fr Archimedes (fast degradation) stents will be considered for dominant strictures in the common bile duct. Balloon dilatation (4mm or 6mm diameter) to facilitate stent placement will be allowed. If stent placement proved impossible after 2 ERCPs, then this will be classified as a failure. After the procedure, patients will be kept overnight for observation and intravenous antibiotics.

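### Clinical success is defined by liver tests alone, so a patient whose study stricture is re-treated after week 2 and whose tests are improved at week 12 counts as a success of the stent.

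*Protocol*

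**What the plan says.** Protocol section 2, Secondary endpoints, gives the whole definition: "Clinical success is defined by improvement in liver function tests (LFT) by 20% at week 2 and week 12". It does not mention repeat procedures or require that a stent was placed.

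Other places bear on it:

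- Primary endpoint: "Technical success and safety of biodegradable stent placement at ERC". Technical success is kept apart from clinical success.
- Secondary endpoints also list "Cumulative recurrence -free rate of primary high grade strictures within 12 months", and stricture recurrence, morbidity and local complications over 12 months.
- Research hypothesis: remodelling of strictures "with fewer interventions in comparison to balloon dilation alone with a comparable risk profile to current therapy".
- Stenting: "If stent placement proved impossible after 2 ERCPs, then this will be classified as a failure". The endpoint to which this failure belongs is not named. The same section says: "Balloon dilatation (4mm or 6mm diameter) to facilitate stent placement will be allowed".
- Sample size: a cited prospective study "demonstrated a re-intervention free rate of 55% at 12 months for balloon dilatation". The section then assumes 15% re-intervention-free at 12 months for the biodegradable stent.
- Background: the stated aim of endoscopic treatment is to improve cholestasis by relieving the obstruction.

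**The concern.** A repeat procedure acts directly on the variable that scores success. By the protocol's own account, endoscopic treatment relieves obstruction and so improves cholestasis, which is what the liver tests measure. The sample size section takes for granted that some patients will be re-treated within 12 months.

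Take a patient who has a 20% improvement at week 2, whose stent occludes at week 6, who has the stricture dilated or stented again, and whose tests are improved at week 12. This patient meets the definition at both visits. The stent has failed, yet the patient is counted in its favour. The error runs in one direction and grows with the failure rate. In a single-group study, no concurrent arm scored by the same rule would reveal it. This is also the protocol's only measure labelled clinical success, so it is likely to be read as the main statement of benefit.

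**Working it through.** **The plan's own figure.** The sample size section gives 21 per group for 55% against 15%, two-sided alpha 0.05 and 80% power, and 50 in total after 15% dropout.

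- Arcsine formula: n = 2(1.960 + 0.842)² / h², with h = 2·asin(√0.55) − 2·asin(√0.15). This gives 20.5, rounded up to 21. The pooled normal formula gives 22. Power at 21 per group is 79.8%.
- Dropout: 42 / 0.85 = 49.4, rounded up to 50.

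The stated figures reproduce. They concern re-intervention-free survival and do not depend on how clinical success is defined.

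**Does the definition admit re-treated patients?** There are two ways to read the two time points.

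| Patient | Improvement needed at both visits | Visits scored separately |
|---|---|---|
| No response at week 2, re-treated, improved at week 12 | Not a success | Week-12 success |
| Response at week 2, stent fails, re-treated, improved at week 12 | Success | Success at both |

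The second row is misclassified at week 12 on either reading. The first row is misclassified only if the visits are scored separately.

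**How many patients could be re-treated by week 12?** The protocol gives no such rate. Assume a constant hazard and let S be the 12-month re-intervention-free rate. The share re-treated by week 12 is r = 1 − S^(12/52).

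| S | Source | r | Of 21 |
|---|---|---|---|
| 0.55 | Balloon dilatation rate, Sample size | 1 − 0.55^(12/52) = 12.9% | 2.7 |
| 0.15 | Stent rate as written, Sample size | 1 − 0.15^(12/52) = 35.5% | 7.4 |
| 0.85 | If 15% was meant as the event rate | 1 − 0.85^(12/52) = 3.7% | 0.8 |

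**How far would the success rate be overstated?** Overstatement = r × q, where q is the share of re-treated patients who meet the liver-test rule. The protocol does not give q.

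- With q = 1, the overstatement equals r: about 4, 13 or 35 points. These are upper bounds for each assumed r.
- A middle case, r = 15% and q = 50% (both assumed), gives 0.15 × 0.50 = 7.5 points, or 21 × 0.075 = 1.6 patients.
- One patient in 21 is 1/21 = 4.8 points.

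For scale, the exact 95% confidence interval for 14 of 21 is 43% to 85%.

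**The case against.** Several points on the other side have force.

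- **The statistical analysis plan may settle it.** Handling of re-treatment is often left there, and scoring tests regardless of later treatment is a recognised choice. But the protocol does more than stay silent: it states what clinical success is. An analysis plan that added a re-intervention condition would change that definition. Scoring regardless of later treatment also fits poorly with a hypothesis about needing fewer procedures.
- **Both visits may be required.** This narrows the problem, because a patient with no week-2 response cannot be rescued later. It does not remove patients who responded first and failed afterwards.
- **Failure shows elsewhere.** A stent that needs re-treatment should appear under recurrence or complications. That does not correct the success rate: the same patient can be a recurrence and a clinical success.
- **The effect may lie within the noise.** With 21 patients the interval is wide, and the middle case is under two patients. But this error is systematic, and the interval does not allow for it.

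Two stronger readings are tempting and are not supported. A reader might infer that a patient who was dilated but never stented is counted as a success. The Stenting section does call impossible placement a failure, and such a patient fails the primary endpoint. What is open is only whether that failure carries over to clinical success. A reader might also extend the point to the week-52 imaging: "MRCP at week 52 to assess for stricture remodelling with improvement in liver biochemistry". No success rule is attached to that assessment, so there is no definition to correct.

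**Conclusion.** The point holds for patients re-treated after an initial response, on either reading of the two visits. The definition counts them as successes, and the error favours the stent. It concerns a secondary endpoint and changes no sample size, alpha or power.

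The size cannot be fixed from the protocol. About 4% to 35% re-treated by week 12 (0.8 to 7.4 of 21), with 13% (2.7 of 21) at the balloon rate, rests on a constant hazard that the protocol does not support or rule out. As a bound on the overstatement, it also assumes that every re-treated patient meets the threshold and would otherwise have failed it. A reader might take 13 to 35 points as the expected bias. That is not warranted: the lower figure uses the balloon rate, and the upper takes the 15% re-intervention-free rate for the stent at face value, although it conflicts with the hypothesis of fewer interventions. What is certain is that each misclassified patient moves the rate by 4.8 points.

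**What to change.** Amend the definition in Secondary endpoints as follows:

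1. Clinical success at each visit is a 20% improvement in liver tests with no further biliary intervention on the study stricture between successful stent placement and that visit. Patients re-treated in that interval are scored as non-success.
2. The interval starts at successful placement, whether at the first or the permitted second ERCP. Without this time origin, a patient stented at the second ERCP could be scored as a failure because of the first. Naming the study stricture keeps procedures on other ducts from counting.
3. The placement failure described under Stenting also counts as non-success for this endpoint.
4. The rate based on liver tests alone is reported as a sensitivity analysis, so the biochemical result is not lost.

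The cost is a few sentences and a slightly less favourable reported rate. The dates and sites of repeat procedures are needed in any case for the recurrence endpoint and for the hypothesis about the number of interventions. No visit, sample size or treatment changes.

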#### **Participants**

Eligible patients with a diagnosis of PSC according to the European association for study of liver 2009 criteria, ascertained with MRCP, ERC, percutaneous transhepatic cholangiography and/or liver biopsy were between 18-75 years of age and fulfilled at least 1 of the following 5 criteria sets: (1) serum bilirubin  $> 3$  times the upper limit of normal (ULN); (2) progression of right upper quadrant pain (RUQP), pruritus, fatigue and/or fever attributed to acute bacterial cholangitis by at least 1 grade according to the Amsterdam Cholestatic Complaints score (ACCS) within the last month, together with a 50% increase of total bilirubin and/or ALP within

the last 4 months and absolute value > 1.2 times the ULN; (3) increase of 20% or more of total bilirubin and/or ALP within the last 4 months and absolute value > 1.2 times the ULN, together with a documented dominant appearing stricture on MRCP or ERC < 4 months before screening; (4) progression of RUQP, pruritus, fatigue and/or fever attributed to bacterial cholangitis by at least 1 grade within the last month, together with total bilirubin and/or ALP > 1.2 times the ULN and a documented stricture on recent MRCP or ERC < 4 months before screening; (5) summed cholestatic complaints score of  $\geq 3$ , or pruritus  $\geq 2$ , or RUQP  $\geq 2$  at screening, together with total bilirubin and/or ALP > 1.2 times the ULN and a documented dominant stricture on recent MRCP or ERC < 4 months before screening. A dominant stricture was defined as any stricture arising in the extrahepatic or left/right main ducts that was deemed functionally relevant by the treating endoscopist/radiologist.

All participants will provide written consent. Eligible patients will be:

- Patients with PSC without evidence of decompensation of chronic liver disease (ascites, hepatic encephalopathy).
- Evidence of a high grade stricture (>75% narrowing) on Magnetic resonance cholangiopancreatography (MRCP) with bile duct dilatation with no evidence of decompensation of liver disease and no other possible causes of elevated liver tests.
- Participants will be aged 18 years or older.
- The decision to proceed to an ERC will be in the Liver Xray/autoimmune MDT as per standard of care (SOC).

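### The only defined liver-test endpoint is an unexplained yes/no cut at 20% improvement, which costs precision in 21 patients and gives a single-group rate with no natural reference value

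*Protocol*

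**What the plan says.** The protocol's Secondary endpoints list states: "Clinical success is defined by improvement in liver function tests (LFT) by 20% at week 2 and week 12". The symptom score and the SF-36 in the same list carry no cut-point. The Participants section also mentions improved liver biochemistry alongside the week 52 MRCP, but defines no measure there. The responder rule is therefore the only liver-test outcome that the protocol defines.

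The primary endpoint is "Technical success and safety of biodegradable stent placement at ERC", and the design is a "Single centre, open-label, single group pilot study with a follow up of 12 months". On numbers, the Sample size section says: "We aim to enroll 21 prospective patients into Group A and use a historical cohort for Group B". Its power statement concerns the 12-month re-intervention-free rate and not liver tests.

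A figure of 20% also appears among the eligibility criteria: "increase of 20% or more of total bilirubin and/or ALP within the last 4 months and absolute value > 1.2 times the ULN". The protocol does not link that entry criterion to the outcome cut.

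**The concern.** Liver tests are continuous measurements. The rule records a patient with a 19% fall in the same way as one whose values doubled, and a 20% fall in the same way as an 80% fall. In a large trial that may be a tolerable simplification. In 21 patients it widens the uncertainty considerably, and a success rate does not say how large the change was.

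The second difficulty comes from the single group. Ordinary variation between two measurements will carry some patients past a 20% improvement even if the group as a whole does not move. The share that does so depends on the variability, which the protocol does not give. The reader of an uncontrolled success rate therefore has no fixed value to set it against.

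**Working it through.** **The plan's own figure.** The sample size rests on re-intervention-free rates of 55% and 15%. With a pooled two-proportion formula, "to attain a power of 80% and a 2-sided alpha level of 0.05", n = [1.960·√(2·0.35·0.65) + 0.842·√(0.55·0.45 + 0.15·0.85)]² / 0.40² = 21.1, or 22 after rounding up; the arcsine version gives 20.5, or 21. So "yielded a sample size of $n = 21$ per group" reproduces, and 42/0.85 = 49.4 gives the stated total of 50. None of this concerns liver tests. The protocol gives no SD, effect size, expected response rate or test for them, so the liver-test inputs below are assumptions shown as a range.

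**1. Information kept by the cut.** If the underlying change is normal and a share q of patients passes the cut, the large-sample efficiency of the responder rate relative to the mean is φ(c)²/[q(1−q)], where φ is the standard normal density and c is the normal quantile of q.

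| Responder rate q | φ(c) | Efficiency | 21 × efficiency |
|---|---|---|---|
| 50% | 0.399 | 0.64 | 13.4 |
| 30% | 0.348 | 0.58 | 12.1 |
| 20% | 0.280 | 0.49 | 10.3 |

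The 21 patients count as about 13, 12 or 10.

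**2. What the intervals look like.** For 11 responders of 21 (52%), the exact 95% interval is 30% to 74%. For a mean log ratio, the half-width is t(0.975; 20)/√21 = 2.086/4.583 = 0.455 SD. With an assumed log-SD of 0.5 that is 0.228, so an observed ratio to baseline of 0.75 has a 95% interval of 0.75·e^(−0.228) to 0.75·e^(0.228), or 0.60 to 0.94.

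**3. Successes with no median change.** Let log(follow-up/baseline) be normal with mean 0 and SD s. The chance of a fall of at least 20% is p0 = Φ(ln 0.8/s), with ln 0.8 = −0.223.

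- s = 0.4: Φ(−0.558) = 0.288
- s = 0.5: Φ(−0.446) = 0.328
- s = 0.6: Φ(−0.372) = 0.355

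So 29% to 36% would be called successes at one time point.

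**4. Power, if the single group were tested.** For a true median fall f, the t-test has noncentrality √21·[−ln(1−f)]/s. The responder probability is p1 = Φ([ln 0.8 − ln(1−f)]/s). The exact binomial test against p0 at one-sided 2.5% needs at least 11, 12 or 13 responders for s = 0.4, 0.5 or 0.6. Because counts are discrete, its true size is 1.97%, 1.84% or 1.23%. A fair comparison runs the t-test at that same size.

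| Fall | s | p1 | t-test at 2.5% | t-test at matched size | Responder test | Loss at matched size |
|---|---|---|---|---|---|---|
| 25% | 0.4 | 0.564 | 88.0% | 85.5% | 72.5% | 13.0 |
| 25% | 0.5 | 0.551 | 70.8% | 65.7% | 51.7% | 14.0 |
| 25% | 0.6 | 0.543 | 55.2% | 42.5% | 31.7% | 10.7 |
| 30% | 0.4 | 0.631 | 97.3% | 96.4% | 89.1% | 7.3 |
| 30% | 0.5 | 0.605 | 87.5% | 84.1% | 70.9% | 13.2 |
| 30% | 0.6 | 0.588 | 73.6% | 61.9% | 47.9% | 14.0 |

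The loss is about 7 to 14 points. Without matching the size, the same rows would show about 8 to 26 points, but part of that comes from the conservatism of the exact test and not from the cut.

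**The case against.** The strongest reply is that there is no power here to lose. The endpoint is secondary in a single-group pilot whose primary aim is technical success and safety, and the protocol plans no test of it. That stands. A reader might infer that the cut costs this trial 10 to 25 points of power; the documents do not support that, because the figure depends on an assumed SD and effect, and its upper end shrinks once test sizes are matched.

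A reader might also infer that a liver-test comparison with Group B would be weakened. In a two-group model with 21 per group and 80% power on the continuous scale, the responder comparison would have 57% to 61% if 20% to 50% of controls met the cut. But the protocol brings in the historical cohort only in the re-intervention calculation. It does not say that liver tests will be compared, or that historical values at these weeks exist. Nor does it say that the pilot exists to measure the liver-test effect.

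It can further be said that clinical success per patient needs some threshold, that 20% echoes an entry criterion, and that a continuous summary may sit in an analysis plan not shown here. A responder rate is indeed a legitimate clinical summary, and nothing prevents reporting continuous change as well. But an entry trigger for a rise does not by itself justify an outcome cut for a fall. The point is also not one of missing analysis detail: the protocol itself fixes the cut as the endpoint, and a later plan could only add to it.

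**Conclusion.** The point holds as a minor one about precision and interpretation. The protocol makes an unexplained 20% cut its only defined liver-test outcome. Under a normal model this leaves 21 patients with the information of about 10 to 13, if between 20% and 50% respond. The resulting rate has no natural reference value in a single group: with log-SDs of 0.4 to 0.6, 29% to 36% would succeed without any median change. A power loss of about 7 to 14 points applies only if the endpoint were tested in the single group, under those SDs and a true fall of 25% or 30%.

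All these figures treat one liver test at one time point. The endpoint's wording does not settle which tests must improve, or whether both weeks must be met, so the loss for the rule as finally applied could differ. A ratio to baseline has 1 as its no-change value, but it would not by itself separate a stent effect from natural fluctuation in patients selected with raised values.

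**What to change.** In the Secondary endpoints list, define the liver-test endpoint as the change from the pre-procedure value in ALP and in total bilirubin, the two analytes that the eligibility criteria already use. Report week 2 and week 12 separately, each as a geometric mean ratio to baseline with a 95% confidence interval. Keep the 20% improvement rate as a supportive summary. Adjust for log baseline only if a comparison with Group B is made and its values exist.

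Confirm that liver tests are scheduled at week 12. The Participants section names them at week 2 and, in general terms, around week 52, but not at week 12. The flow chart may list them, but it is not shown.

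The cost is the rewording of one secondary endpoint, with no extra patients. No extra samples are needed either, provided the week 12 tests are already scheduled. A ratio is less immediate to clinicians than a success rate, but the rate would still be reported.
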